**Methods of analysis**

The data will be statistically processed with Statistica 10.0 software. The following tests will be used to compare data with normal distribution: two-tailed Student's test and ANOVA. The Mann-Whitney test and ANOVA will be used to compare non-normally distributed data. The regression analysis will be used for quantitative efficacy data. The categorical data will be processed using the Fisher's exact test, Yates-corrected Pearson's test  $\chi^2$  and Cochran-Mantel-Haenszel test.

**PK analysis**

The PK analysis will include data of all volunteers who have received one dose of BCD-131 or reference drugs. If a subject has had more than two PK serum samples missed / lost / spoilt and skipped blood sampling time points more than twice, his/her data will not be included in the PK analysis.

**PD analysis**

The PD analysis will include data of all volunteers who have received one dose of BCD-131 or reference drugs. If a subject has had more than two PK serum samples missed / lost / spoilt and skipped blood

	
sampling time points more than twice, his/her data will not be included in the PD analysis.
 
Safety analysis
 
The safety analysis will include all patients who have received one dose of the test/reference drug.
 
Immunogenicity analysis
 
The immunogenicity analysis will include data of all volunteers who have received one dose of BCD-131 or reference drugs. If a subject has had serum samples taken on Day 1 and Day 50 missed / lost / spoilt, his/her data will not be included in the immunogenicity analysis.

--	--

1. INTRODUCTION

The Statistical Analysis Plan (SAP) provides a detailed analysis plan and steps of study report preparation for the clinical trial BCD-131-1.

2. GOALS AND OBJECTIVES

2.1. Purpose

To evaluate the tolerability, safety, pharmacokinetics, pharmacodynamics and immunogenicity of single ascending doses of BCD-131 in healthy volunteers as compared to Mircera® and Aranesp®.

2.2. Objectives

Study objectives (Stage I):

1. Establish the frequency and severity of adverse events following the administration of single ascending doses of BCD-131 to healthy volunteers.
2. Establish key pharmacokinetic (PK) parameters ($AUC_{0-1176\text{ h}}$, $AUC_{0-\infty}$, C_{\max} , T_{\max} , $T_{1/2}$, K_{el} and CL) of BCD-131 following the administration of single ascending doses of the drug product to healthy volunteers.
3. Establish pharmacodynamic (PD) parameters ($AUEC_{0-1176\text{ h}}$, $AC-E_{\max}$) of BCD-131 based on the absolute reticulocyte count and Hb values in the blood of healthy volunteers following the administration of single ascending doses of BCD-131.
4. Study serum levels of binding antibodies (BAbs) in the blood of healthy volunteers following the subcutaneous administration of single ascending doses of BCD-131.
5. Establish main PK ($AUC_{0-1176\text{ h}}$, $AUC_{0-\infty}$, C_{\max} , T_{\max} , $T_{1/2}$, K_{el} and CL) and PD parameters ($AUEC_{0-1176\text{ h}}$, $AC-E_{\max}$ based on changes in the absolute reticulocyte count and Hb levels in the blood) as well as immunogenicity of therapeutic doses of Mircera® and Aranesp® given as subcutaneous injections to healthy volunteers.
6. Establish a safe dose of subcutaneous BCD-131 to be used at stage II of the study.

Study objectives (Stage II):

CONFIDENTIAL

Version 1.0 dated 21-Sep-2015

Page 4 of 21

1. Establish key pharmacokinetic parameters ($AUC_{0-1176\text{ h}}$, $AUC_{0-\infty}$, C_{\max} , T_{\max} , $T_{1/2}$, K_{el} and CL) of BCD-131 given as a single subcutaneous or intravenous injection to healthy volunteers at a dose established at stage I of the study.
2. Establish key pharmacodynamic parameters ($AUEC_{0-1176\text{ h}}$, $AC-E_{\max}$ based on changes in the absolute reticulocyte count and Hb levels in the blood) of BCD-131 given as a single subcutaneous or intravenous injection to healthy volunteers at a dose established at stage I of the study.
3. Establish the frequency and severity of adverse events and evaluate the level of BAbs to BCD-131 given as a single subcutaneous or intravenous injection to healthy volunteers at a dose established at stage I of the study.
4. Establish subcutaneous and intravenous doses of BCD-131 to be used in a phase II clinical study.

3. STUDY DESIGN

3.1 Design

Stage I

Stage I of clinical study BCD-131-1 is an open-label, non-randomized clinical study of pharmacokinetics, pharmacodynamics, tolerability, safety and immunogenicity of the novel drug product given to healthy volunteers at ascending doses (Phase 1, a traditional “3+3” design). Also, at stage I the investigators will evaluate the PK and PD parameters of the closest analogues of BCD-131 (Mircera[®] and Aranesp[®]) given as subcutaneous injections at therapeutic doses.

Volunteers (no more than 54 subjects at stage I) will be included in the study after they have signed an informed consent form, completed an examination at screening (no more than 14 days) and received the approval of the investigator confirming their eligibility for the study.

Evaluation of pharmacokinetics, pharmacodynamics and safety of ascending doses of BCD-131

The evaluation of pharmacokinetics, safety and tolerability of BCD-131 will be conducted in 8 cohorts:

1. Cohort 01 will include no more than 6 volunteers who will receive a single subcutaneous injection of BCD-131 at a dose of 0.05 µg/kg body weight.
2. Cohort 02 will include no more than 6 volunteers who will receive a single subcutaneous injection of BCD-131 at a dose of 0.15 µg/kg body weight.
3. Cohort 03 will include no more than 6 volunteers who will receive a single subcutaneous injection of BCD-131 at a dose of 0.40 µg/kg body weight.
4. Cohort 04 will include no more than 6 volunteers who will receive a single subcutaneous injection of BCD-131 at a dose of 1.05 µg/kg body weight.
5. Cohort 05 will include no more than 6 volunteers who will receive a single subcutaneous injection of BCD-131 at a dose of 1.70 µg/kg body weight.
6. Cohort 06 will include no more than 6 volunteers who will receive a single subcutaneous injection of BCD-131 at a dose of 2.75 µg/kg body weight.
7. Cohort 07 will include no more than 6 volunteers who will receive a single subcutaneous injection of BCD-131 at a dose of 4.45 µg/kg body weight.

Volunteers will be included in the study in a consecutive order. First, three volunteers will be included in Cohort 01 to receive a single subcutaneous injection of BCD-131 at a calculated starting safe dose of 0.05 µg/kg. If during 14 days after the injection these volunteers do not develop any treatment-emergent Grade 3–4 adverse events, the next three volunteers will be included in the study (Cohort 02). The further inclusion algorithm is as follows:

If during 14 days after the injection of BCD-131 the subjects do not develop any treatment-emergent Grade 3-4 AEs (DLT), the next cohort consisting of three volunteers will be included in the study to receive an escalated dose of BCD-131 (Cohort 03, Cohort 04, Cohort 05 etc.).

If during 14 days after the injection of BCD-131 only one volunteer (of three) develops a treatment-emergent Grade 3-4 AE (DLT), three more healthy volunteers will be included in this cohort to receive BCD-131.

If two subjects develop treatment-emergent Grade 3-4 AEs (DLT), the dose of BCD-131 which resulted in these events is considered to be the maximum tolerated dose (MTD). No further dose escalating is performed.

Thus, the dose-limiting toxicity is assessed as close as possible to the time of drug administration during the first 14 days after the injection. However, follow-up of volunteers does not stop; it will continue up to Day 50 from the moment of injection and include the monitoring of volunteers' health as well as safety and PK parameters of BCD-131.

Evaluation of pharmacokinetics, pharmacodynamics and safety of subcutaneous therapeutic doses of Mircera® and Aranesp®

Simultaneously with the evaluation of pharmacokinetics, pharmacodynamics and safety of ascending doses of BCD-131, the investigators will evaluate the pharmacokinetics, pharmacodynamics and safety of subcutaneous therapeutic doses of Mircera® and Aranesp®. For this purpose, 12 more volunteers will be included in the study.

After having been randomized in a 1:1 ratio, the volunteers will be assigned to 2 groups. Six volunteers in Group 1 will receive a single subcutaneous injection of Mircera® at a dose of 1.20 µg/kg (Day 1). Six volunteers in Group 2 will receive a single subcutaneous injection of Aranesp® at a dose of 0.45 µg/kg (Day 1).

After the last volunteer enrolled in stage I of the study has completed all the procedures specified in the Study Protocol, an interim analysis of the data obtained will be performed. Based on the comparison of pharmacokinetics, pharmacodynamics and safety of different doses of the test drug and active comparators, the investigators will establish a dose of BCD-131 which ensures PD effects similar to those of the closest analogues (Mircera®, Aranesp®) given as subcutaneous injections at therapeutic doses. The established dose of BCD-131 will be used at stage II of the study.

Subjects will be asked to stay at the study site for the first 24 h after the injection because multiple blood samples are to be collected over this period.

Regardless of the group/cohort to which a volunteer has been assigned, s/he will be followed-up for 50 days during which 16 visits will be performed.

Stage II

Stage II of the study aims to further evaluate pharmacokinetics, pharmacodynamics and safety of subcutaneous and intravenous injections of BCD-131 at a dose which ensures PD effects similar to those of the closest analogues (Mircera[®], Aranesp[®]) given as subcutaneous injections at therapeutic doses. For this purpose, 12 volunteers will be included in the study after they have signed an informed consent form, completed an examination at screening (no more than 14 days) and received the approval of the investigator confirming their eligibility for the study.

After having been randomized in a 1:1 ratio, the volunteers will be assigned to 2 groups.

- Six volunteers in Group 1 will receive a single intravenous injection of BCD-131 at a dose established at stage I of the study (Day 1).
- Six volunteers in Group 2 will receive a single subcutaneous injection of BCD-131 at a dose established at stage I of the study (Day 1).

Subjects will be asked to stay at the study site for the first 24 h after the injection because multiple blood samples are to be collected over this period. Regardless of the group/cohort to which a volunteer has been assigned, s/he will be followed-up for 50 days during which 16 visits will be performed.

3.2 Time Points for Blood Sampling to Evaluate PK at Stage I of the Study

In the groups of volunteers receiving BCD-131 and Mircera[®], blood sampling for the PK evaluation will be performed as follows:

1. PK1-1 — 5 min before the injection of BCD-131/Mircera[®]
2. PK2-1 — 30 ± 5 min after the injection of BCD-131/Mircera[®]
3. PK3-1 — $2 \text{ h} \pm 10 \text{ min}$ after the injection of BCD-131/Mircera[®]
4. PK4-1 — $8 \text{ h} \pm 15 \text{ min}$ after the injection of BCD-131/Mircera[®]
5. PK5-1 — $24 \text{ h} \pm 20 \text{ min}$ after the injection of BCD-131/Mircera[®]
6. PK6-1 — $48 \text{ h} \pm 30 \text{ min}$ after the injection of BCD-131/Mircera[®]
7. PK7-1 — $72 \text{ h} \pm 30 \text{ min}$ after the injection of BCD-131/Mircera[®]
8. PK8-1 — $96 \text{ h} \pm 60 \text{ min}$ after the injection of BCD-131/Mircera[®]
9. PK9-1 — $120 \text{ h} \pm 60 \text{ min}$ after the injection of BCD-131/Mircera[®]
10. PK10-1 — $168 \text{ h} \pm 60 \text{ min}$ after the injection of BCD-131/Mircera[®]

11. PK11-1 — 216 h ± 120 min after the injection of BCD-131/Mircera®
12. PK12-1 — 288 h ± 120 min after the injection of BCD-131/Mircera®
13. PK13-1 — 336 h ± 120 min after the injection of BCD-131/Mircera®
14. PK14-1 — 504 h ± 120 min after the injection of BCD-131/Mircera®
15. PK15-1 — 672 h ± 120 min after the injection of BCD-131/Mircera®
16. PK16-1 — 840 h ± 120 min after the injection of BCD-131/Mircera®
17. PK17-1 — 1008 h ± 120 min after the injection of BCD-131/Mircera®
18. PK18-1 — 1176 h ± 120 min after the injection of BCD-131/Mircera®

In the group of volunteers receiving Aranesp®, blood sampling for the PK evaluation will be performed as follows:

1. PK1-1 — 5 min before the injection of Aranesp®
2. PK2-1 — 30 ± 5 min after the injection of Aranesp®
3. PK3-1 — 2 h ± 10 min after the injection of Aranesp®
4. PK3-1 — 8 h ± 15 min after the injection of Aranesp®
5. PK5-1 — 16 h ± 20 min after the injection of Aranesp®
6. PK6-1 — 24 h ± 20 min after the injection of Aranesp®
7. PK7-1 — 36 h ± 30 min after the injection of Aranesp®
8. PK8-1 — 48 h ± 30 min after the injection of Aranesp®
9. PK9-1 — 72 h ± 30 min after the injection of Aranesp®
10. PK10-1 — 96 h ± 60 min after the injection of Aranesp®
11. PK11-1 — 120 h ± 60 min after the injection of Aranesp®
12. PK12-1 — 168 h ± 60 min after the injection of Aranesp®
13. PK13-1 — 216 h ± 120 min after the injection of Aranesp®
14. PK14-1 — 288 h ± 120 min after the injection of Aranesp®
15. PK15-1 — 336 h ± 120 min after the injection of Aranesp®
16. PK16-1 — 504 h ± 120 min after the injection of Aranesp®
17. PK17-1 — 672 h ± 120 min after the injection of Aranesp®
18. PK18-1 — 840 h ± 120 min after the injection of Aranesp®

19. PK19-1 — 1008 h ± 120 min after the injection of Aranesp®
20. PK20-1 — 1176 h ± 120 min after the injection of Aranesp®

3.3 Time Points for Blood Sampling to Evaluate PK at Stage II of the Study

1. PK1-2 — 5 min before the injection of BCD-131
2. PK2-2 — 15 ± 3 min after the injection of BCD-131
3. PK3-2 — 30 ± 5 min after the injection of BCD-131
4. PK4-2 — 60 ± 5 min after the injection of BCD-131
5. PK5-2 — 2 h ± 10 min after the injection of BCD-131
6. PK6-2 — 4 h ± 15 min after the injection of BCD-131
7. PK7-2 — 8 h ± 15 min after the injection of BCD-131
8. PK8-2 — 24 h ± 20 min after the injection of BCD-131
9. PK9-2 — 48 h ± 30 min after the injection of BCD-131
10. PK10-2 — 72 h ± 30 min after the injection of BCD-131
11. PK11-2 — 96 h ± 60 min after the injection of BCD-131
12. PK12-2 — 120 h ± 60 min after the injection of BCD-131
13. PK13-2 — 168 h ± 60 min after the injection of BCD-131
14. PK14-2 — 216 h ± 120 min after the injection of BCD-131
15. PK15-2 — 288 h ± 120 min after the injection of BCD-131
16. PK16-2 — 336 h ± 120 min after the injection of BCD-131
17. PK17-2 — 504 h ± 120 min after the injection of BCD-131
18. PK18-2 — 672 h ± 120 min after the injection of BCD-131
19. PK19-2 — 840 h ± 120 min after the injection of BCD-131
20. PK20-2 — 1008 h ± 120 min after the injection of BCD-131
21. PK21-2 — 1176 h ± 120 min after the injection of BCD-131

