8.2. Description of the Statistical Methods to be Employed

Quantitative Data

The following quantitative data will be analyzed in the study:

Pharmacokinetics:

- Plasma concentration of drug,
- Area under plasma concentration curve,
- Time (e.g., maximum plasma concentration time, half-life)

- Elimination parameters (e.g. clearance, terminal rate constant)

Pain Assessment:

- VAS score

Safety:

- CBC results,
- Blood chemistry results,
- Vital signs;
- ECG findings,
- Urea analysis results,
- Skin disorders size at the sites of venipuncture,
- Skin disorders lifetime at the sites of venipuncture.

Pharmacodynamics:

- absolute reticulocyte count.
- Hb level.
- Area under effect curve «absolute reticulocyte count — time».
- Area under effect curve «Hb level — time».
- Time (e.g. the time of the maximum increase of absolute reticulocyte count vs. baseline).

The statistical analysis will include two-tailed hypothesis testing; the chosen significance level is 0.05.

Quantitative variables will be tested for normality using the Shapiro-Wilk test.

Normally distributed quantitative variables will be tested using the two-sample Student's t-test, Welch's t-test, and ANOVA.

Non-normally distributed quantitative variables will be tested using the Mann-Whitney U-test, the Wilcoxon test, the Kruskal-Wallis test, and the Friedman test.

Normally distributed quantitative data will be described using the following descriptive statistics: mean, SD, CV, min, and max. Non-normally distributed quantitative data will be described using the following descriptive statistics: median, quartiles, CV, min, and max.

Categorical Data

The following categorical data will be analyzed in the study:

Safety:

- Skin disorders sort at the sites of venipuncture.
- Rate and severity grades of AEs/SAEs,
- Rate of Grade 3-4 AEs,
- Frequency of local reactions (total and by skin disorder type).
- Frequency of early study termination cases by AEs/SAEs.

Categorical data will be processed using frequency tables, contingency tables, the Fisher's exact test, the test of equal frequencies, Pearson's χ^2 test, and the Cochran-Mantel-Haenszel test. Percentages or proportions will be used to describe categorical data.

The Benjamini-Yekutieli correction for multiple testing will be used.

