Statistical methods will be chosen according to the type of initial data and their distribution. Appropriate statistical tests will be established after the data collection has been completed because the type of data distribution, sample homogeneity, etc. are unknown before the study start. For appropriate data processing, the list of statistical methods used may expand during the analysis.

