8.3. Accounting for missing, unavailable or doubtful data, outliers

All information specified in the e-CRFs should be supported by relevant data in source documents.

After entering all data into the electronic database, a database specialist checks it for inconsistencies, errors, and missing data points. The Clinical Study Database Manager or Medical Expert of JSC BIOCADC generates queries to correct error data or to request missing data; the queries are site-specific and subject-specific (i.e., individual queries are generated for each subject). The Clinical Study Monitor will send queries to the study site by fax or email. The queries should be resolved by the investigator within five business days from the date they have been submitted to the study site. Copies of responses to queries must be kept at the study site; original responses must be stored at JSC BIOCADC.

When responses to queries are received from investigators, the database specialist checks it for inconsistencies, errors, and missing data points. When all data at all study sites have been collected and entered, the database is closed. Afterwards, statistical processing can be started.

Missing, unused, and spurious data will not be substituted.

Spurious and unevaluable data are revealed during the outlier analysis by examination of Mahalanobis or Cook distance, visual analysis of scatter plots and box plots.

All actions taken to handle missing, unevaluable, spurious data and outliers before/during the statistical analysis will be described in the Clinical Study Report.

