8.5. Multivariate Comparison and Multiplicity

Refer to Section 8.2.

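### The stage II dose is to match the comparators' PD effect, but the plan includes no estimate of dose relative to comparator with an interval

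*SAP*

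**What the plan says.** SAP 3.1 (Design), in the same words as the Protocol's Study Design section, states that once the last stage I volunteer has finished, "an interim analysis of the data obtained will be performed". From a comparison of PK, PD and safety across BCD-131 doses and comparators, the investigators are then to "establish a dose of BCD-131 which ensures PD effects similar to those of the closest analogues". That dose goes into stage II.

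SAP 8.2 sets out the tools for quantitative data:

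- **Tests:** "The statistical analysis will include two-tailed hypothesis testing; the chosen significance level is 0.05". The tests named are Student's t, Welch, ANOVA, Mann-Whitney, Wilcoxon, Kruskal-Wallis and Friedman.
- **Summaries:** "Normally distributed quantitative data will be described using the following descriptive statistics: mean, SD, CV, min, and max". For non-normal data, the median and quartiles replace the mean and SD.
- **Open clause:** "the list of statistical methods used may expand during the analysis".

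Neither document names a confidence interval, or a ratio or difference between a dose and a comparator. The Protocol's Methods of analysis paragraph mentions regression for quantitative efficacy data but gives no model, and SAP 8.2 does not repeat it.

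**The concern.** The decision asks whether a dose resembles a comparator. The named inferential methods ask whether it differs. With three subjects on one side and six on the other, a test of difference can easily miss a sizeable difference, so a non-significant result says little about resemblance.

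The quantity the investigators need is the effect of each dose relative to Mircera and to Aranesp, and how precisely that is known. The plan does not ask for it. The stage II dose depends on this judgement, and through stage II so does the objective of setting phase II doses.

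**Working it through.** **1. Group sizes (SAP 6).** Seven doses × (3 + 3) = 42. Adding 6 + 6 comparator subjects gives 54, the stated stage I maximum. Adding 6 + 6 at stage II gives 66, the stated total. SAP 3.1 speaks of eight cohorts but lists seven doses, and 54 and 66 reproduce only with seven. Without expansion, stage I has 7 × 3 + 12 = 33 subjects in 9 groups. The documents give no power, margin or variability, so there is no such figure to reproduce.

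**2. Precision of a dose-to-comparator ratio, 3 v 6.** The between-subject CV is an assumption, shown from 20% (favourable) to 50%.

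- Log-scale SD: s = √ln(1 + CV²)
- Standard error of the log ratio: SE = s × √(1/3 + 1/6) = 0.707 s
- 90% CI factor: exp(t × SE), with t(0.95; 7 df) = 1.895 pairwise and t(0.95; 24 df) = 1.711 pooled (33 − 9 = 24)

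| Assumed CV | s | SE | Pairwise ×/÷ | Pooled ×/÷ |
|---|---|---|---|---|
| 20% | 0.198 | 0.140 | 1.30 | 1.27 |
| 30% | 0.294 | 0.208 | 1.48 | 1.43 |
| 40% | 0.385 | 0.272 | 1.68 | 1.59 |
| 50% | 0.472 | 0.334 | 1.88 | 1.77 |

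For a cohort expanded to six, the pairwise factors at CV 30/40/50% are 1.36/1.50/1.64. On a difference scale at 3 v 6, the half-width is 1.895 × 0.707 = 1.34 SD pairwise or 1.711 × 0.707 = 1.21 SD pooled.

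**3. Which AUEC the comparison would use.** SAP 4.2 bases AUEC on the change in reticulocyte count. The SAP 8.4 formula integrates the count itself and subtracts no baseline. The choice matters for a ratio. Assume that the lower of two effects is an average rise of 20% or 60% of baseline, and that the other effect is twice as large:

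- Rise of 20%: raw AUEC ratio = (1 + 0.40)/(1 + 0.20) = 1.17
- Rise of 60%: raw AUEC ratio = (1 + 1.20)/(1 + 0.60) = 1.38

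A two-fold difference in effect therefore appears as a raw ratio of about 1.2 to 1.4. The CVs in step 2 are meant for a baseline-corrected effect, so those factors do not carry over to the raw AUEC, which would have a different CV.

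**The case against.** **Most of the information is already planned.** With three subjects, the mean, minimum and maximum fix all three values. With mean, SD and group size, anyone can compute a difference and its interval. The study is an open-label, unpowered 3+3 design, the dose choice also weighs PK and safety, and stage II then observes the chosen dose in 12 more subjects. All of this stands. The gap is a planned estimate, not missing data.

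**Regression is named.** The Protocol mentions it, and SAP 10 declares no deviation from Protocol methods. That softens the point, but no model, contrast or interval is specified. The open clause in SAP 8.2 permits additions without committing to any.

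**Stronger readings that the documents do not support:**

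- A reader might infer that a dose will be called similar because a test is non-significant. At 3 v 6, a log-scale t-test would miss a true two-fold difference in 18/41/57% of trials at CV 30/40/50%. The plan contains no such rule, the means will be in view, and at CV 20% the figure is 1.3%. These rates describe the tests, not the dose decision.
- A reader might infer that PD differences can never reach significance. The smallest exact Mann-Whitney p at 3 v 6 is 2/84 = 0.0238, and the most lenient Benjamini-Yekutieli threshold is 0.0240 for four tests and 0.0219 for five. That matters only if the correction covers PD tests, the family has at least five tests, and exact Mann-Whitney is used. "The Benjamini-Yekutieli correction for multiple testing will be used" closes the Categorical Data part of SAP 8.2, while SAP 8.5 says only "Refer to Section 8.2", so the scope is unclear.
- A reader might infer that the interim analysis is forbidden, because SAP 8.3 says "When all data at all study sites have been collected and entered, the database is closed. Afterwards, statistical processing can be started". SAP 3.1 plainly intends that analysis and fixes its timing. SAP 8.3 reads as general data-management text, so this needs a clarifying sentence only.

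**Conclusion.** The concern holds in a limited form. The plan sets a similarity question for the stage II dose, names only tests of difference as inference, and plans no estimate of dose relative to comparator with an interval. Uncertainty could be derived from the planned summaries, so this is an inexpensive improvement to how the dose decision is supported. It is not a defect that invalidates the decision.

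The size depends on the assumed CV. A 90% interval at 3 v 6 runs from about ×/÷ 1.3 at CV 20% to about ×/÷ 1.8 to 1.9 at CV 50%. The pooled figures also assume similar variance across groups and full escalation through seven unexpanded cohorts. The difference between SAP 4.2 and SAP 8.4 has to be settled first, because a ratio of raw AUECs hides much of a difference in effect.

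**What to change.** 1. **Reconcile the endpoint.** Make SAP 4.2 and the SAP 8.4 formula agree on whether reticulocyte AUEC is corrected for baseline.
2. **Make the interim PD comparison an estimate (SAP 8.2).** For reticulocyte AUEC and AC-Emax, report each dose relative to Mircera and to Aranesp with a 90% CI, using variance pooled over groups, alongside the group summaries. Fix the scale (ratio or difference) before data are seen. A log ratio needs positive values, whereas a difference can always be computed.
3. **State that a non-significant test is not evidence of similarity.**
4. **Minor clarifications.** Describe a stage I data cut and lock in SAP 8.3, and list the interim analysis in SAP 5, which now mentions only the end-of-study report. Say whether Benjamini-Yekutieli covers the PD tests.

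The cost is SAP wording and a little analysis, with no new subjects or samples. The downside is up to 7 × 2 × 2 = 28 intervals, wide and unadjusted, which show uncertainty and do not prove similarity. Pooling adds an equal-variance assumption. No dose or similarity margin is proposed, and the choice stays with the investigators.
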